**Table 2. Management of Toxicity and Blinatumomab Dosage Adjustments**

Toxicity	Grade	Action	
		Patient Weight	
		≥ 45 Kg	< 45 Kg
Cytokine Release Syndrome (CRS)	Grade 3	Withhold blinatumomab until resolved, then restart blinatumomab at 9 mcg/day. Escalate to 28 mcg/day after 7 days if the toxicity does not recur.	Withhold blinatumomab until resolved, then restart blinatumomab at 5 $\mu\text{g}/\text{m}^2/\text{day}$ . Escalate to 15 $\mu\text{g}/\text{m}^2/\text{day}$ after 7 days if the toxicity does not recur.
	Grade 4	Discontinue blinatumomab permanently	
Neurological Toxicity	Seizure	Discontinue blinatumomab permanently if more than one seizure occurs	
	Grade 3	Withhold blinatumomab until no more than Grade 1 (mild) and for at least 3 days, then restart blinatumomab at 9 mcg/day. Escalate to 28 mcg/day after 7 days if the toxicity does not recur. If the toxicity occurred at 9 mcg/day, or if the toxicity takes more than 7 days to resolve, discontinue blinatumomab permanently.	Withhold blinatumomab until no more than Grade 1 (mild) and for at least 3 days, then restart blinatumomab at 5 $\mu\text{g}/\text{m}^2/\text{day}$ . Escalate to 15 $\mu\text{g}/\text{m}^2/\text{day}$ after 7 days if the toxicity does not recur. If the toxicity occurred at 5 $\mu\text{g}/\text{m}^2/\text{day}$ , or if the toxicity takes more than 7 days to resolve, discontinue blinatumomab permanently.
	Grade 4	Discontinue blinatumomab permanently	
Other Clinically Relevant Adverse Reactions	Grade 3	Withhold blinatumomab until no more than Grade 1 (mild), then restart blinatumomab at 9 mcg/day. Escalate to 28 mcg/day after 7 days if the toxicity does not recur. If the toxicity takes more than 14 days to resolve, discontinue blinatumomab permanently.	Withhold blinatumomab until no more than Grade 1 (mild), then restart blinatumomab at 5 $\mu\text{g}/\text{m}^2/\text{day}$ . Escalate to 15 $\mu\text{g}/\text{m}^2/\text{day}$ after 7 days if the toxicity does not recur. If the toxicity takes more than 14 days to resolve, discontinue blinatumomab permanently
	Grade 4	Discontinue blinatumomab permanently	

## 4.0 Patient Eligibility

### 4.1 Inclusion Criteria:

1. Patients 1-70 years of age.
2. Patients with B-lineage ALL in a) hematologic complete remission (CR) beyond CR1 at time of transplant; b) primary induction failure defined as requiring more than one line of induction therapy; c) positive minimal residual disease defined by positive flow >0.01% before or after transplant; or d) high risk cytogenetic or molecular features consisting of Ph-like phenotype, detection of BCR-ABL transcript by PCR with a sensitivity of 1/10,000, or detection of the t(9;22) translocation in any metaphases by cytogenetics at time of transplant, or presence of the MLL gene before or after transplant.
3. Received an allogeneic HCT within the last 100 days. Enrollment within 30-100 days after transplant, and after adequate recovery of counts defined as ANC  $\geq 0.5 \times 10^9/L$  without daily use of myeloid growth factor and platelet  $> 20 \times 10^9/L$  without platelet transfusion within 1 week, and adequate organ function to receive blinatumomab defined as creatinine clearance greater than 30 ml/min (or greater than 60 ml/min/1.73), ALT/AST  $< 5 \times$  ULN and serum bilirubin  $< 3 \times$  ULN.
4. Performance status of 0, 1, or 2. Karnofsky (or Lansky for subjects < 16 years old) performance status  $\geq 50$ .

### 4.2 Exclusion criteria:

1. Relapsed ALL defined as >5% malignant blasts in bone marrow or peripheral blood.
2. Active GVHD requiring systemic steroid therapy. Medications for GVHD prophylaxis are acceptable.
3. Systemic steroid therapy unless for physiologic replacement
4. Uncontrolled disease/infection as judged by the treating physician
5. Active ALL in the central nervous system (CNS), as defined by  $\geq 5$  leukocytes per  $\mu L$  with identifiable blast cells in the CSF (CNS 3 disease), and/or the presence of cranial-nerve palsies.
6. Pregnant or nursing women

## 5.0 Treatment Plan

5.1 This is an open-label, single-arm, phase II clinical study.

5.2 All patients will be registered through Core. All of the enrolled subjects' concomitant medications will be collected and readily available in the MDACC electronic medical record and will not be entered into the CRF.

5.3 Patients will receive blinatumomab as continuous intravenous infusion over 4 weeks.

Since this study includes children and adults, dosing will be weight and BSA-based as per FDA approved dosing guidelines:

**For patients  $\geq 45$  kg**, the dose is 28 mcg/day administered as a continuous infusion on days 1-28 of each cycle.

**For patients  $< 45$  kg** the dose is 15 mcg/m^2/day (maximum 28 mcg/day) administered as a continuous infusion on days 1-28 of each cycle

All patients will receive 4 cycles of blinatumomab, with first cycle administered within the first 3 months following HCT, and then at 6 (+/- 2 weeks), 9 (+/- 2 weeks), and 12 (+/- 2 weeks) months following HCT (day of hematopoietic progenitor cell infusion). This schedule was selected to allow for treatment with blinatumomab during the one year following transplant when patients are at risk for relapse while the GVL effect is maturing and becoming robust.

5.4 GVHD prophylaxis will be as institutional standard.

5.5 CNS prophylaxis will be as institutional standard. However, craniospinal radiotherapy for prophylaxis post HCT is not permitted.

5.6 Tyrosine kinase inhibitor (TKI) use for patients with Ph+ ALL will be left to the investigator's discretion.

## 6.0 Study Evaluations

### 6.1 Pretreatment Evaluation

**Table 3. Pre-treatment evaluation schedule**

Procedure	Comments	Schedule
Informed Consent	Obtain standard informed consent approved by IRB	Within 14 days before therapy
Medical History	History of present illness, known allergies, prior cancer history as far as traceable including ALL regimens and drugs uses, and past medical/ surgical history as far as relevant.	Within 14 days of therapy
Physical Examination	Vital signs (temperature, heart rate, respiratory rate, blood pressure) and performance status.	Within 14 days of therapy
Concomitant Medications	Document concomitant medications, excluding prn and supportive care medications	Within 14 days of therapy
Hematology	CBC with differential and platelet count	Within 14 days of therapy
Biochemistry	at least creatinine, total bilirubin, uric acid, LDH, SGPT or SGOT, tacrolimus.	Within 14 days of therapy
Pregnancy test	Serum or urine, if female and /of child-bearing potential only	Within 14 days of therapy
Bone marrow	Aspirate and/or biopsy with flow cytometry for confirmation of diagnosis; cytogenetics	Within 30 days of therapy
Peripheral blood	Chimerism assessment	Within 30 days of therapy
Lumbar puncture	To assess for CNS disease, as clinically indicated	Within 30 days of therapy
Imaging studies	Chest X-ray and/or PET/CT as clinically indicated	Within 30 days of therapy

## 6.2 Evaluation during study

**Table 4. Evaluation During Study**

Procedure	Comments	Schedule
Hematology	CBC with differential and platelet count	Weekly during each cycle
Biochemistry	at least creatinine, total bilirubin, SGPT or SGOT, tacrolimus	Weekly during each cycle
Physical Examination	Focused physical examination, including assessment for GVHD	Prior to each treatment cycle, and at study completion
Bone marrow	Aspirate and/or biopsy, MRD by multicolor flow cytometry, cytogenetics	Prior to each treatment cycle, and at study completion will be per the PI or treating physician discretion
Peripheral blood	Multiparameter FCI for immune reconstitution and PB chimerism	Prior to each treatment cycle, and at study completion will be per the PI or treating physician discretion
Optional Procedure: Peripheral blood	For banking in [name] laboratory at MDACC	Prior to each treatment cycle, at day 7 (+/- 2 days), day 14 (+/- 2 days) and at completion of each treatment cycle.

## 6.3 Evaluation of Toxicity

Toxicities will be graded according to the NCI Expanded Common Toxicity Criteria, version 4.

## 7.0 Criteria for Removal from the Study

7.1 Completion of study at 1 year.

7.2 Non-compliance by the patient with protocol requirements.

7.3 Occurrence of CTCAE grade 4 adverse event probably or definitely related to blinatumomab.

7.4 An infusion interruption of more than 2 weeks due to an adverse event related to blinatumomab.

7.5 Occurrence of a CNS-related adverse event probably or definitely related to blinatumomab, and meeting one or more of the following criteria:

- More than 1 seizure
- A CNS-related CTCAE Grade 4 adverse event
- A CNS-related adverse event leading to treatment interruption that requires more than one week to resolve to CTCAE Grade  $\leq 1$
- A CTCAE Grade 3 CNS-related adverse event leading to treatment interruption that occurred at a dose of 9 $\mu$ g/day

## **8.0 Statistical Considerations**

### **8.1 Patient Characteristics**

Demographic and baseline characteristics will be summarized for all patients. Categorical measures will be summarized using frequencies and percentages, while continuous variables will be summarized using mean, standard deviation, median, minimum, and maximum.

### **8.2 Primary Objectives**

The primary objective in this trial is feasibility. Treatment-related toxicities attributable to blinatumomab, an excess rate of acute GVHD, and an excess rate of secondary graft failures will be the parameters to determine feasibility. The successful completion of the trial without reaching stopping rules will indicate that the primary objective of the trial was met. Cumulative incidence time to GVHD will be computed from the date of allogeneic HCT to the date of event. The cumulative incidence (CI) of GVHD will be determined using the competing risks method. The competing risks included will be relapse and death, and patients who do not experience GVHD or relapse and are still alive at the last follow-up date will be censored at that date.

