#### 8.3.5 Continuous Toxicity Monitoring

Continuous monitoring of toxicity will be assessed for all treated patients, beginning with the first cohort of five patients. Assuming a prior beta distribution of (0.6, 1.4), the study will terminate if the  $\Pr(\delta_t > 0.30 | \text{data}) > 0.85$ , where  $\delta_t$  is the toxicity rate attributable to the treatment. Toxicities are defined as any 1) grade 3-4 acute GVHD greater than 30%, 2) secondary graft failure >30%, or 3) NRM within one cycle of blinatumomab (i.e., 30 days). The decision rule for terminating for toxicity is presented in Table 5 and the operating characteristics for this rule are presented in Table 6. The method used to produce the decision rule and operating characteristics was designed by Thall, Simon, and Estey (1995).

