**Table 5. Stopping Boundaries**

Total number of patients	Stop if this many patients have toxicity:
1-4	Never stop with this many patients
5	3-5
6-7	4-7
8-10	5-10
11-13	6-13
14-16	7-16
17-18	8-18
19-21	9-21
22-24	10-24
25-27	11-27
28-29	12-29
30	Always stop with this many patients

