**Table 6. Operating Characteristics**

True % of DLTs	Pr (stopping early)	Median Sample Size (interquartile)
0.10	0.01	30 (30, 30)
0.20	0.10	30 (30, 30)
0.30	0.36	30 (13, 30)
0.40	0.72	13 (5, 30)
0.50	0.94	5 (5, 13)

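### Not reaching the stopping boundary is taken as meeting the feasibility objective, so feasibility can be declared at 10 to 12 toxicities in 30, where the plan's own posterior puts the rate more likely than not above 30%

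*Combined protocol and SAP*

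**What the plan says.** Section 8.2 names feasibility as the primary objective. It lists toxicities attributable to blinatumomab and then states that "an excess rate of acute GVHD, and an excess rate of secondary graft failures will be the parameters to determine feasibility". The decision criterion follows: "The successful completion of the trial without reaching stopping rules will indicate that the primary objective of the trial was met".

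Section 8.3.5 supplies the stopping rule: "Assuming a prior beta distribution of (0.6, 1.4), the study will terminate if the" posterior probability of a toxicity rate above 0.30 is greater than 0.85. On timing it says: "Continuous monitoring of toxicity will be assessed for all treated patients, beginning with the first cohort of five patients".

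Table 5 turns the rule into counts, from 3 of 5 up to 12 of 28 or 29. Its row for 30 patients carries no count and reads only "Always stop with this many patients". Table 6 gives early-stopping probabilities of 0.01, 0.10, 0.36, 0.72 and 0.94 at true rates of 0.10 to 0.50.

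No section sets a threshold to be met at the end of the trial, and none plans an estimate or interval for the composite rate that drives the rule.

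**The concern.** A safety boundary and a success criterion answer different questions. The boundary asks whether the data are convincing enough of excess toxicity to halt accrual, and it rightly demands strong evidence. Section 8.2 then takes the absence of that strong evidence as the sign that feasibility was met. Between convincing evidence of excess and reasonable evidence of acceptability lies a range of inconclusive results, and the plan counts all of them as success.

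The primary conclusion could then run against the trial's own posterior: a report could state that feasibility was shown while the same prior, limit and data make a rate above the limit the more likely state.

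**Working it through.** **Inputs.** Prior Beta(0.6, 1.4), limit 0.30 and cutoff 0.85 (8.3.5); monitoring from five patients (8.3.5); stopping counts and maximum of 30 patients (Table 5); stopping probabilities (Table 6). Each patient is treated as one yes/no outcome, known before the next look.

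**Step 1: reproduce the plan's figures.** With x toxicities in n patients the posterior is Beta(0.6 + x, 1.4 + n − x). The boundary is the smallest x with Pr(rate > 0.30) > 0.85. For example, 2/5 gives 0.626 (continue) and 3/5 gives 0.875 (stop); 11/29 gives 0.801 (continue) and 12/29 gives 0.890 (stop). All Table 5 counts for n = 5 to 29 are reproduced.

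An exact binomial recursion, with a look after every patient from 5 to 29, gives:

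| True rate | Pr(stop), recomputed | Table 6 |
|---|---|---|
| 0.10 | 0.010 | 0.01 |
| 0.20 | 0.097 | 0.10 |
| 0.30 | 0.358 | 0.36 |
| 0.40 | 0.718 | 0.72 |
| 0.50 | 0.938 | 0.94 |

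The medians and quartiles in Table 6 match as well. Looks only every five patients do not match (0.289 at 0.30 and 0.617 at 0.40).

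**Step 2: posterior at 30 patients.** The posterior is Beta(0.6 + x, 31.4 − x), with mean (0.6 + x)/32.

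| Toxicities | Observed | Posterior mean | 95% credible interval | Pr(rate > 0.30) |
|---|---|---|---|---|
| 9/30 | 30% | 0.300 | 0.157–0.467 | 0.479 |
| 10/30 | 33% | 0.331 | 0.182–0.500 | 0.632 |
| 11/30 | 37% | 0.363 | 0.208–0.533 | 0.764 |
| 12/30 | 40% | 0.394 | 0.235–0.565 | 0.863 |

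The highest count that can be reached without stopping is 12: 11/29 continues, patient 30 then has a toxicity, and Table 5 has no count at 30 to catch it. That result is above the plan's own 0.85 cutoff.

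**Step 3: how often this happens.** From the same recursion, the probability of completing with each count:

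| True rate | Complete | 10/30 | 11/30 | 12/30 | 10 to 12 | Share of completed trials |
|---|---|---|---|---|---|---|
| 0.20 | 0.903 | 0.0212 | 0.0060 | 0.0007 | 0.028 | 3% |
| 0.30 | 0.642 | 0.0847 | 0.0413 | 0.0083 | 0.134 | 21% |
| 0.40 | 0.282 | 0.0690 | 0.0522 | 0.0163 | 0.137 | 49% |

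The last column is the sum divided by the completion probability, for example 0.1375/0.2816 = 0.488.

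**Step 4: if the 0.85 formula also applies at n = 30.** A count of 12 then stops, and only 10/30 and 11/30 remain: 0.0212 + 0.0060 = 0.027 at 20%, 0.0847 + 0.0413 = 0.126 at 30%, and 0.0690 + 0.0522 = 0.121 at 40%. Completion becomes 0.903, 0.634 and 0.265. The problem shrinks slightly but stays.

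**The case against.** The strongest reply is that nothing is hidden. The success rule is stated openly, Table 6 stands beside the boundary, and this is a single-arm phase II trial of at most 30 patients with a feasibility aim. A reader might see feasibility claims in 64% of trials at a true 30% rate and 28% at 40%, and infer a concealed error of that size. The documents do not support that: these figures are one minus Table 6 (1 − 0.36 and 1 − 0.72). They show a lenient criterion. The conflict with the posterior is the smaller 13% to 14%, and at a true 30% rate 79% of completed trials end at 9/30 or fewer, where there is no conflict.

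A reader might also infer that the plan claims proof of safety. Section 8.2 says only that completion will indicate success. Nor do 10/30 and 11/30 show excess toxicity: their credible intervals reach down to 0.18 and 0.21.

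It is also fair to say that several component rates will be reported: cumulative incidence of GVHD (8.2) and of non-relapse mortality (8.3.3), and adverse events by frequency and percentage (8.3.4). Graft failure is a listed serious adverse event (9.4). These summaries do not give the composite rate, however, and none of them bears on the feasibility decision.

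These replies limit the size and wording of the point. They do not remove it, because no other criterion in the documents would block a feasibility claim at 10 to 12 toxicities in 30.

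**Conclusion.** The point holds in a limited form. The monitoring rule is correctly computed and suitable as a safety rule. Used as the sole test of the primary objective, it lets feasibility be declared when the posterior probability of exceeding the limit is 0.63 to 0.86. This is confined to 10 to 12 toxicities in 30. It is uncommon if the true rate is 20%, happens in about one trial in seven at 30% or 40%, and makes up about half of the trials that complete at 40%.

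The result assumes a maximum of 30 patients, per-patient scoring before each look (the reading that reproduces Table 6), and the plan's own prior. The 12/30 case also assumes that Table 5 governs at 30 patients; Step 4 shows the result without it. If looks came only every five patients, the chance of completing with 10 or more toxicities would rise to 3.6%, 19.0% and 23.3% at true rates of 20%, 30% and 40%.

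A reader might conclude that a final posterior cutoff of 0.50 is required. The documents do not support any particular cutoff. The defect is that none is set and that the conclusion is not tied to an estimate.

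**What to change.** 1. Reword 8.2 so that not reaching the boundary means only that monitoring did not show excess toxicity.
2. Apply the 0.85 rule at 30 patients too, so that 12 or more toxicities is not called feasible. This moves the claim probability from 0.642 to 0.634 at a true 30% rate and from 0.282 to 0.265 at 40%; at 20% it stays at 0.903 to three decimals or within 0.001.
3. Make the primary result the composite toxicity rate with its 95% credible interval and the final probability that it exceeds 0.30, under the Beta(0.6, 1.4) prior, and base the feasibility conclusion on these.
4. Have the sponsor pre-specify any final cutoff, with its operating characteristics. Two illustrations, keeping Table 5:

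| True rate | Current 8.2 | Pr(rate > 0.30) at most 0.50 (9/30 or fewer) | Pr(rate > 0.30) at most 0.20 (7/30 or fewer) |
|---|---|---|---|
| 0.20 | 0.90 | 0.88 | 0.73 |
| 0.30 | 0.64 | 0.51 | 0.26 |
| 0.40 | 0.28 | 0.14 | 0.04 |

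5. Clarify the per-patient event in 8.3.5 first. That section writes a rate, greater than 30%, into the GVHD and graft-failure events themselves, and its list does not include the general blinatumomab-attributable toxicities that 8.2 names. Until this is reconciled, the composite cannot be computed cleanly.

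The cost is SAP wording and one posterior summary. Sample size and the Table 5 boundaries for 5 to 29 patients do not change. A final cutoff lowers the chance of a claim when toxicity is acceptable: by 2.8 points at a true 20% rate for the 0.50 illustration (0.903 to 0.875), and by 17 points for the stricter one (0.90 to 0.73).

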## 1.0 Objectives

1.1 Primary: To assess the feasibility of blinatumomab post allogeneic hematopoietic cell transplantation (HCT) as consolidation therapy in patients with B-lineage acute lymphoblastic leukemia (ALL). Toxicities attributable to blinatumomab, acute GVHD, and secondary graft failure will be the parameters to define feasibility.

1.2 Secondary:

1.2.1 To evaluate the progression-free survival (PFS) rate at 1-year for patients with ALL compared to contemporary patient cohort.

1.2.2 To evaluate other efficacy endpoints such as overall survival (OS) and minimal residual disease (MRD) negativity rate in patients treated with blinatumomab for consolidation therapy.

1.2.3 To evaluate, non-relapse mortality (NRM) and chronic GVHD.

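### The cumulative incidence of GVHD in section 8.2 starts at transplant rather than at first blinatumomab dose, so it mixes pre-exposure with on-drug GVHD and misses later flares

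*Combined protocol and SAP*

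**What the plan says.** Objective 1.1 makes acute GVHD part of feasibility: "Toxicities attributable to blinatumomab, acute GVHD, and secondary graft failure will be the parameters to define feasibility". Section 8.2 repeats this as "an excess rate of acute GVHD, and an excess rate of secondary graft failures will be the parameters to determine feasibility", and gives no reference rate for the excess.

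The estimate follows in the same paragraph: "Cumulative incidence time to GVHD will be computed from the date of allogeneic HCT to the date of event". Relapse and death are the competing risks, and "patients who do not experience GVHD or relapse and are still alive at the last follow-up date will be censored at that date". The sentence gives no grade, does not restrict to acute GVHD, and has no rule for an episode before treatment.

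The decision rule is separate: "The successful completion of the trial without reaching stopping rules will indicate that the primary objective of the trial was met". Section 8.3.5 applies that rule to all treated patients and counts grade 3-4 acute GVHD among its toxicities.

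On timing, inclusion criterion 3 sets "Enrollment within 30-100 days after transplant", and section 5.3 places the first cycle within three months of transplant. Exclusion 2 reads "Active GVHD requiring systemic steroid therapy. Medications for GVHD prophylaxis are acceptable". Exclusion 3 also bars systemic steroids given for any purpose beyond physiologic replacement.

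Chronic GVHD is a secondary objective (1.2.3): "To evaluate, non-relapse mortality (NRM) and chronic GVHD". Section 8.3 gives it no analysis of its own.

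**The concern.** The parameter is meant to describe GVHD under blinatumomab, but the clock starts 30 or more days before any patient can receive the drug. The eligibility criteria leave room for patients whose GVHD resolved before entry, or was never treated with systemic steroids. Their event date then precedes exposure. A competing-risks curve with one event per patient has no place for a second episode, so a flare on drug in these patients goes uncounted.

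Two further problems follow. Nobody who died before entry can be in the study, so the interval from transplant to entry contains no deaths by construction. And because GVHD is not qualified, a reader of the results could not tell whether the curve shows acute GVHD, chronic GVHD or both, or at what grade.

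At stake is the interpretation of the figure reported under Primary Objectives. Its level could suggest harm that the drug did not cause, while its rise after treatment start would leave out flares in patients who had GVHD before.

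**Working it through.** **1. The plan's own figures.** The documents state no GVHD rate and no precision for this curve, so there is no figure to reproduce for it. The related figures are those of the stopping rule. With a Beta(0.6, 1.4) prior, the boundary at n patients is the smallest r with Pr(rate > 0.30 | r of n) > 0.85. At n = 5 the probability is 0.8745 for r = 3 and 0.6261 for r = 2, so the boundary is 3, as in Table 5. Every boundary from n = 5 to 29 agrees. With a look after each patient from the fifth, exact early-stopping probabilities at true rates 0.10 to 0.50 are 0.0103, 0.0966, 0.3576, 0.7184 and 0.9384. Table 6 gives 0.01, 0.10, 0.36, 0.72 and 0.94. The rule is sound on its own terms and is not in dispute here.

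**2. Can pre-dose GVHD be an event?** Origin: transplant (8.2). Entry: day 30-100 (4.1). Barred at entry: active GVHD needing systemic steroids, and non-physiologic systemic steroids (4.2). Not barred: resolved GVHD, or GVHD managed without systemic steroids. So yes.

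**3. Illustrative size.** Let g be the share with GVHD before first dose and d the risk of new or recurrent GVHD on drug. Both are assumed. Take d to be the same with or without earlier GVHD, ignore competing risks, and use N = 30 (last row of Table 5).

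- From-transplant curve: g + (1 − g)d
- Events before exposure: 30g
- On-drug episodes counted: 30(1 − g)d
- On-drug flares not counted: 30gd

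For d = 0.20, the on-drug total is 30 × 0.20 = 6 patients:

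| g | Curve reads | Pre-dose events | On-drug counted | On-drug not counted |
|---|---|---|---|---|
| 0.10 | 0.10 + 0.90 × 0.20 = 0.28 | 3 | 5.4 | 0.6 |
| 0.20 | 0.20 + 0.80 × 0.20 = 0.36 | 6 | 4.8 | 1.2 |
| 0.30 | 0.30 + 0.70 × 0.20 = 0.44 | 9 | 4.2 | 1.8 |
| 0.40 | 0.40 + 0.60 × 0.20 = 0.52 | 12 | 3.6 | 2.4 |

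Over d = 0.10 to 0.30, the curve runs from 0.19 (g = 0.10, d = 0.10) to 0.58 (g = 0.40, d = 0.30), and uncounted flares from 0.3 to 3.6 patients.

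**4. Direction.** The level exceeds d by g(1 − d). The part of it that arises on drug falls short of d by gd. The curve therefore overstates on-drug GVHD in its level and understates it in its post-dose rise.

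**5. Why 8.3.5 needs the same window.** Section 8.3.5 sets no time window for GVHD, although it speaks of a rate attributable to treatment. Only if pre-dose grade 3-4 episodes were counted would the rule be affected. With an on-drug toxicity rate of 0.20 and an assumed pre-dose share s, the counted rate is 1 − (1 − 0.20)(1 − s). For s = 0, 0.05, 0.10, 0.15 and 0.20 this is 0.20, 0.24, 0.28, 0.32 and 0.36, and early stopping has probability 0.10, 0.18, 0.29, 0.43 and 0.58.

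**The case against.** The strongest reply is that this curve decides nothing. Section 8.2 ties the primary objective to finishing without crossing the stopping rule, and 8.3.5 does not bar a grade 3-4 acute flare in a patient with earlier GVHD. That stands. A reader might infer that on-drug flares cannot count towards the primary outcome; the documents do not support this.

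Nor is on-drug GVHD invisible elsewhere. Section 9.1 starts adverse event collection at first dose, asks for onset date and maximum grade, and records pre-existing conditions that worsen on treatment. Section 8.3.4 summarises adverse events, GVHD is not on the list of uncollected events in 9.3, and Table 4 has it assessed before each cycle. It would go too far to say that the plan cannot reveal GVHD provoked by blinatumomab. Yet 9.1 also shows the mismatch: it captures the exacerbation, whereas the curve in 8.2 counts the old episode and loses the exacerbation.

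It is also fair that 8.2 names acute GVHD shortly before the estimate, so the unqualified term may mean acute GVHD. That the curve pools acute and chronic GVHD, or counts only a first episode of any type, is an inference. What the text supports is that type, grade and recurrence are undefined.

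Finally, PFS, OS and NRM also start at transplant (8.3.1, 8.3.3), so the origin is consistent within the plan and suits comparison with other from-transplant rates. That is a reason to keep the curve as a supplement. It does not make it a measure of GVHD on drug.

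**Conclusion.** The point holds for the cumulative incidence estimate in 8.2. Its transplant origin is explicit, and the eligibility criteria admit patients with GVHD before first dose. It does not extend to the feasibility decision, and a reader should not conclude that the trial could be declared feasible or infeasible because of this curve.

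The size cannot be fixed from the documents. With 10-40% of 30 patients having GVHD before first dose, 3-12 events would precede exposure. With 20% on-drug risk as well, the curve would read about 28-52%. Both rates are assumptions without a source in the protocol, refer to GVHD of any grade, and ignore competing risks. If no enrolled patient had earlier GVHD, the miscounting would vanish, but the death-free interval before entry and the undefined event would remain. The change should be made; the design and sample size are not in question.

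**What to change.** In section 8.2:

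- Start the GVHD clock at the first blinatumomab dose, with relapse and death as competing risks.
- Define the event as new-onset or worsened acute GVHD after first dose. State that return of a resolved episode, or a rise above the grade present at first dose, qualifies.
- Give a separate curve for grade 3-4 acute GVHD.
- Keep the from-transplant curve as a descriptive supplement.

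In section 8.3.5, state the same after-first-dose window for acute GVHD. At present it has no new-onset, worsening or after-first-dose condition, so changing 8.2 alone would leave two definitions.

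Under objective 1.2.3, report chronic GVHD as its own curve.

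In Table 3, add GVHD status and maximum grade before first dose as a baseline item. The table does not explicitly ask for GVHD history, and adverse event collection begins only at first dose, so the protocol cannot be assumed to capture this already.

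The cost is a few lines of wording, one baseline item and one or two extra curves. The main figure would no longer be directly comparable with rates counted from transplant; the supplementary curve covers that.
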